**Dietary Education Intervention with Wechat Model Will  
Impact on Dietary Protein Intake in Patient Treated  
With Peritoneal Dialysis**

NCT: 02426580

April 30, 2017

Study Design

Study Type: (select one)
 
 Clinical Interventional       Clinical Interventional
 
 Non-clinical (i.e., benchwork, in-vitro, animal model)       Other (explain):

Does the proposed research require an Investigational New Drug (IND)/Investigational Device Exemption (IDE) application (US), a Clinical Trial Application (CTA) (Canada and EU), and/or any other similar regulatory filing?
 
 Yes       No      Explain the basis for your determination: we have cell phones and free download software of wechat

Pathology, disease state, or condition to be treated/studied and incidence:
 
End-stage renal disease (ESRD) patients were treated with peritoneal dialysis. The peritoneal dialysis prescription: 3-4 daily exchanges of 2L dialysate, 16-24 hours a day. Dialysate: 1.5% or 2.5% glucose in dialysate and the concentration of calcium in dialysate is 1.25mmol/L.

Study Population (ages, gender, relevant disease states):
 
Age of 18 to 65 years and no limitation of sex. The patients were diagnosed as ESRD.
 
Key Inclusion Criteria: 1. All patients followed at the PD center that successful completed training and have received treatment for at least 1 month. 2. The life expectancy will be more than one year. 3. All patients will provide written informed consent. (1) Aged between 18 and 65 years old; (2) had been on PD for more than one month in medically stable condition; (3) no peritonitis within one month; (4) All the participants or their family members were required to own a Smartphone and to be able to correctly complete the follow up consultations either on Wechat or on phone calls.
 
Key Exclusion Criteria: 1. the patients will be severe ill status and unlikely to survive for 12 months.

Duration of subject participation: 1st December 2014 – 31st December 2017
 
Prospective : April 2015 to April 2017
 
Retrospective: January 2014 to January 2015

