
Total number of subjects to be enrolled: We will enrolled 140 PD patients from the Stern peritoneal dialysis unit in the Third People's Hospital of Chengdu affiliated with Chongqing Medical University
 
Number of study or comparison groups: All patients will be assigned into two groups according to their willing.
 
Intervention group: N=70
 
Controlled group: N=70

Specific details of Treatment/Intervention: (prescription and/or therapy, devices, equipment, solutions, product to be used in conducting study):
 
This will be a 12-month, A combined prospective and retrospective study of dietary education intervention with comprehensive peritoneal dialysis education with emphasis on egg whites based optimal protein intake on Wechat platform compared with a conventional clinic visit education model. At enrollment, patients will be educated with the conventional education model including operation of dialysate, the catheter exit care, complications of PD, record of ultrafiltration and urine volume, basic protein intake (egg white will be added as a

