suitable kind of protein intake) and calorie intake. And then they will be randomly assigned into one of two parallel groups: (1) Control group: Intervention with conventional education every 1-3 months during routing clinical visit ;( 2) Intervention group: wechat delivery of dietary education: Intervention with conventional education will occur every 3 months during routing clinical visit and wechat model of dietary education will occur every 1 month by cellphone. The control group will also receive monthly cell phone calls but without the wechat intervention. The wechat model will provide information on protein, calcium, phosphorus and sodium intake, suggested by the current KDIGO/ KDOQI guideline. The wechat model will include pictures, words, video and voice. Furthermore, we will emphasize the use of egg white protein which may be effective dietary component lowering serum phosphorus without risking malnutrition. The baseline characteristics included the following variables : age, sex, diabetes, cause of kidney disease if known, medication list, comorbid condition list, smoking history, body weight (kilograms), blood pressure , PCR, serum albumin, serum total protein, C-react protein(CRP)、 white blood cell count(WBC), hemoglobin, serum phosphorus, serum calcium, serum sodium, serum magnesium, serum uric acid, intact parathyroid hormone (iPTH), vitamin D, bicarbonate, KT/V, WCC. The study period will be 12 months, with the patients returning every 3 months for measurement of parameters, peritoneal equilibration test (PET), calculation of KT/V and WCC by software, dietary interviews and 3 day dietary recall and conventional education of PD. And we will record the incidence of peritonitis, readmission and switching to hemodialysis and mortality rate. During the course of study, the dose and types of medication could be changed if medically necessary in the view of the treating physician.

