#### **Efficacy Assessments (What data will be collected/utilized?):**

Wechat is available and convenient for all kinds of platforms with a little network traffic fee (less than 10 RMB per month); enjoy group chat and private chat; support voice, photo, video and text messages. Baidu search found that at present 600 million people had registered wechat in China. We will use the software of wechat to send message to our PD patients with the Nutrition knowledge of protein, phosphorus, calcium and sodium. And the messages will be picture or/and video of food model with voice or/and words notes. Egg whites are tasty and readily available with a low phosphorus content and could be a good source for additional protein intake for the PD patients. The outcomes of our study may be the following:(1) The protein intake of PD patients will achieve or be close to the target of 1.2g/kg/d in intervention with wechat group; (2) Changes in parameters of primary endpoints from baseline to last evaluation may be show significant difference between the intervention with wechat group and the control group; (3) The incidence of peritonitis, readmission, switching to hemodialysis and mortality rate may be lower in the intervention with wechat group compared with the control group. Furthermore the limitations of our study are the single center design.

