#### **Statistical Methods (for analyzing primary & secondary endpoints):**

Continuous variables are reported as mean $\pm$ SD. Categorical variables are reported as frequency and percentage. Comparisons between values of intervention with wechat group and values of controlled group at every time points of study will be made. Continuous variables with normal distribution will use analysis of t-test. Continuous variables with abnormal distribution will use analysis of rank-sum test. Categorical variables will use analysis of covariance. Regression analysis will be performed to comparing the levels of primary endpoints, with PCR being the independent variable. Logistic regression analysis will be performed within the secondary endpoints. All statistical tests were conducted at a significance level of  $\alpha = 0.05$ . All the statistical analyses will be conducted with Empower Stats.

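### Logistic regression for the secondary events has no sparse-data rule: if one arm has no deaths, it gives no finite odds ratio or Wald interval

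*Combined protocol and SAP*

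**What the plan says.** Statistical Methods gives one sentence to these outcomes: "Logistic regression analysis will be performed within the secondary endpoints". It names no estimator, covariates, choice of test or fallback for few events. The same paragraph also says "Categorical variables will use analysis of covariance", which is not a method for binary outcomes, and sets alpha at 0.05.

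The documents never define the secondary endpoints. The natural candidates are the events in outcome (3) of Efficacy Assessments: peritonitis, readmission, switching to hemodialysis and death. There the plan expects that "switching to hemodialysis and mortality rate may be lower in the intervention with wechat group". SAP item 3 lists event comparisons without a method and does not include death.

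The group sizes are "Intervention group: N=70" and "Controlled group: N=70", and "The study period will be 12 months". Inclusion requires a life expectancy of over one year. The Key Exclusion Criteria remove anyone for whom "the patients will be severe ill status and unlikely to survive for 12 months" applies.

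**The concern.** Follow-up lasts 12 months, and the entry criteria screen out patients expected to die within that time. Deaths may therefore be few in 70 per arm, and one arm could have none.

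Maximum-likelihood logistic regression on treatment group cannot handle that case. The fitted odds ratio drifts to zero or infinity, its standard error becomes arbitrarily large and the Wald P approaches 1.

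No deaths under WeChat would be the most favourable mortality result possible. Yet the planned model would supply neither an effect estimate nor a usable Wald interval to support the claim in outcome (3). Because the test is also unstated, the P value would depend on a choice made after the data are seen.

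**Working it through.** **Inputs.** From the documents: 70 per arm, 12 months of follow-up, alpha 0.05, logistic regression. Event risks are not given, so a range is assumed. The plan has no event-related figure to reproduce; its only calculation (50 per group, 60 after dropout) concerns PCR and does not enter here.

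**Step 1: one empty arm, 0/70 (WeChat) against 6/70 (control).**
- Maximum-likelihood logistic fit: the log odds ratio has no finite maximum. One fit stopped at about -22 with SE about 15,700, giving Wald P = 0.999. Another, stopped after fewer iterations, gave -18.2 with SE 2,119 and P = 0.993. The values differ only because there is no finite solution to converge to.
- Likelihood-ratio test of the same model: 2 × {[6 ln(6/70) + 64 ln(64/70)] − [6 ln(6/140) + 134 ln(134/140)]} = 2 × (−20.48 + 24.77) = 8.59 on 1 df, P = 0.003.
- Fisher's exact test, two-sided: 2 × C(70,6)/C(140,6) = 0.028.
- Firth (0.5 added to each cell): OR = (0.5 × 64.5)/(70.5 × 6.5) = 0.070, which is finite.

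The pattern does not depend on the count. For 0 against 5, Fisher P is 0.058; for 0 against 10, it is 0.0014. The Wald P stays above 0.99 in both.

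**Step 2: how often an arm is empty.** Let a = (1 − p_control)^70 and b = (1 − p_WeChat)^70. Then P(exactly one empty) = a(1 − b) + b(1 − a), and P(both empty) = ab. For example, at 2% in both arms, a = b = 0.98^70 = 0.243, so exactly one is empty with probability 2 × 0.243 × 0.757 = 0.368 and both with 0.059.

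**Step 3: how often a Fisher-significant benefit would be hidden.** With WeChat empty, Fisher needs at least 6 control events to fall below 0.05. The chance is b × P(control events ≥ 6).

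| Assumed control risk | Equal: exactly one empty | Equal: both empty | Halved: exactly one empty | Halved: both empty | Halved: WeChat empty, control ≥ 6 |
|---|---|---|---|---|---|
| 1% | 50% | 24% | 50% | 35% | 0.01% |
| 2% | 37% | 6% | 50% | 12% | 0.14% |
| 3% | 21% | 1% | 38% | 4% | 0.65% |
| 5% | 5% | 0.1% | 19% | 0.5% | 2.3% |
| 8% | 0.6% | <0.1% | 6% | <0.1% | 2.8% |
| 10% | 0.1% | <0.1% | 2.8% | <0.1% | 2.0% |

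With both arms empty there is no odds ratio to estimate, but also no observed difference.

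**The case against.** Four objections carry weight.

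- **Scope.** A reader might infer that eligibility makes switching to hemodialysis rare as well. The documents do not support that: the survival criteria concern death, no criterion addresses technique failure, and no rate is given. SAP item 3 also joins transplant to switching, which can only raise that count. Nothing shows that peritonitis or readmission is rare. This objection stands, and the point is confined to death unless observed counts show otherwise.
- **The test.** A reader might infer that the logistic model would report an empty WeChat arm as no evidence. That is true of the Wald test only; the likelihood-ratio test of the same model gives 0.003 in the example. The plan names neither test, nor does it say that the fit is ordinary maximum likelihood, although that is the usual meaning of the unqualified term. This stands as a limit on the claim. The missing odds ratio and Wald interval remain whichever test is used.
- **Whether logistic regression is the group comparison at all.** The analysis-of-covariance sentence competes with it, SAP item 3 names no method, and death is absent from that item. This does not remove the problem: neither sentence gives a workable rule for a sparse binary event, and both need replacing.
- **Weight.** The failure would be plain in the output, and the sample size was set for PCR, not for these events. This fairly limits the importance of the point.

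**Conclusion.** The concern holds in limited form. The plan gives no workable analysis for a binary event with an empty arm, and death is the outcome for which its own eligibility rules make that plausible.

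The size depends on assumed risks. Exactly one empty arm has a chance of 21% to 50% at control risks of 1% to 3%, rising at 3% to 38% if WeChat halves the risk. At 5% the chance is 5% (19% if halved), and at 10% it is under 3%.

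The harm is chiefly a missing estimate and interval, together with an open choice among tests that gave 0.003, 0.028 and 0.999 on the same data. A reader might take the 0/70 against 6/70 example as typical and conclude that a real benefit would probably be hidden. The figures do not support this: the chance is at most about 3% if the risk is halved. It reaches about 12% only under an assumed 75% reduction from risks of 8% to 10%.

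The conclusion rests on reading logistic regression as ordinary maximum likelihood and outcome (3) as the secondary endpoints. Both are reasonable inferences, but neither is stated.

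**What to change.** In Statistical Methods, replace both the logistic sentence and the analysis-of-covariance sentence, as they apply to binary events, with:

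*For each binary event, including death, the risk difference between groups is reported with a Newcombe or Miettinen-Nurminen 95% interval and Fisher's exact test. Where regression is used for an event with few cases or an empty arm, Firth's penalised likelihood with profile-likelihood intervals is used.*

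Add death to SAP item 3, and state which events are the secondary endpoints.

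The cost is a few lines of text, with no extra patients or data. Fisher's test is slightly conservative, and the Firth routine may need software other than the named package.

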**Is the study sufficiently powered (adequate sample size) to answer the research question? Explain:**

We tested a sample population of 10 patients treated at the PD center who successfully completed training and were on therapy for at least 3 months. At the time of the first clinic visit, we collected data and calculated mean  $\pm$  SD of PCRs as  $0.834 \pm 0.154$  using SPSS (version1.6). According to sample size counting formula  $N = 2^*[(\alpha+\beta)^*\sigma/\delta]^2$ , we calculated that a total sample size of 50 patients in each group will be needed to detect a significant difference ( $P<0.05$ ) in PCR of  $+0.090$  g/(kg.d) from baseline to last measurement during the study between the wechat group and control group. The sample size (assuming a 20% dropout rate) was estimated at 60 patients in each group. So we think this study is sufficiently powered to answer the research question.

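### The sample size targets a difference in PCR change but uses a single-visit SD, while the planned tests compare raw values and leave the collected baseline PCR unused

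*Combined protocol and SAP*

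**What the plan says.** In the protocol, the sample-size section (under the question whether the study is sufficiently powered) defines its target as a PCR difference of +0.090 g/(kg.d) "from baseline to last measurement during the study between the wechat group and control group". That is a between-group difference in change.

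The variability input is a mean and SD of 0.834 ± 0.154. Its source is given as "We tested a sample population of 10 patients treated at the PD center", and it was measured once: "At the time of the first clinic visit, we collected data and calculated mean". These patients "were on therapy for at least 3 months", whereas the inclusion criteria admit patients after one month. The section gives its formula in symbols, arrives at 50 per group, and raises this to 60 for 20% dropout. The design section enrols 70 per group.

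Statistical Methods describes a different comparison: "Comparisons between values of intervention with wechat group and values of controlled group at every time points of study will be made". For the test itself it says "Continuous variables with normal distribution will use analysis of t-test", with a rank-sum test otherwise. Analysis of covariance is named, but for categorical variables. The one regression described puts PCR on the right-hand side, as the independent variable. The SAP lists nPCR at baseline and after 12 months as separate items and does not link them.

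**The concern.** Three quantities could serve as the PCR result: the difference in 12-month values, the difference in change, and the baseline-adjusted difference. Each has its own SD. The protocol sizes the second with the SD that belongs to the first, plans to test the first, and does not mention the third for PCR.

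Two things follow. The statement that the study is sufficiently powered cannot be checked for a change analysis, because that needs a correlation which the documents do not give. And the planned test discards baseline nPCR, which is recorded on everyone. Under random allocation this costs precision whenever baseline and 12-month PCR are correlated. If patients choose their group, any baseline PCR difference also passes straight into the unadjusted 12-month comparison. The design section assigns patients by their own willingness, while the intervention description says assignment is random.

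Because no single PCR analysis is named, the choice between raw values, change and rank-sum stays open until the data are seen.

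**Working it through.** **Inputs from the documents.** Single-visit SD 0.154 from 10 patients; difference 0.090; 50 per group; 20% dropout; 70 per group enrolled; significance level 0.05, sidedness not stated.

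**Assumptions.** The correlation r between baseline and 12-month PCR is not in the documents and is shown as a range. SDs are taken as equal at both visits, and expected baselines as equal between groups.

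**Step 1: the plan's own figure.** N per group = 2 × [(z_α + z_β) × 0.154 / 0.090]².
- Two-sided 0.05, 80% power: 2 × (2.802 × 1.711)² = 45.96, so 46.
- Two-sided 0.05, 85% power: 52.6, so 53. At 90% power: 61.5, so 62.
- One-sided 0.05, 80% power: 36.2, so 37. At 90% power: 2 × (2.926 × 1.711)² = 50.15.

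Of these, only one-sided 0.05 with 90% power gives about 50, and the section states neither. The 60 is 50 × 1.2; dividing by 0.8 gives 62.5, so 63. Enrolling 70 covers both, and 70 × 0.8 = 56 are expected to remain.

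**Step 2: the SD that belongs to each analysis.**
- Raw 12-month values: 0.154.
- Change score: 0.154 × √(2(1 − r)). This equals 0.154 only at r = 0.5.
- ANCOVA: 0.154 × √(1 − r²).

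Since 1 − r² = (1 − r)(1 + r), it never exceeds 1 or 2(1 − r). Under random allocation, ANCOVA is therefore at least as precise as either alternative, apart from one degree of freedom.

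**Step 3: power for 0.090 with 50 per group** (two-sample t-test, two-sided 0.05; the one degree of freedom for the covariate is ignored).

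| r | SD of change | Power, change | ANCOVA SD | Power, ANCOVA | Power, raw values |
|---|---|---|---|---|---|
| 0.2 | 0.195 | 63% | 0.151 | 84% | 82% |
| 0.4 | 0.169 | 75% | 0.141 | 88% | 82% |
| 0.5 | 0.154 | 82% | 0.133 | 92% | 82% |
| 0.6 | 0.138 | 90% | 0.123 | 95% | 82% |
| 0.7 | 0.119 | 96% | 0.110 | 98% | 82% |

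**Step 4: the number expected to remain.** With 56 per group and r = 0.2, power is 86.5% for raw values, 68% for change and 88% for ANCOVA. A change-score test reaches 80% power only if r is about 0.40 or more; with 50 per group the threshold is about 0.47.

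**Step 5: uncertainty in 0.154.** With 9 degrees of freedom and normality assumed, the 95% limits are 0.154 × √(9/19.02) = 0.106 and 0.154 × √(9/2.70) = 0.281. Over that interval, raw-value power with 50 per group runs from 99% to 35%. At the upper limit, ANCOVA with r = 0.5 has 45% power with 50 per group and 49% with 56.

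**The case against.** The strongest reply is that the test actually planned is adequately sized. Statistical Methods compares values, not changes. For that test 0.154 is the relevant SD, and 50 per group gives about 82% two-sided power at any correlation. The protocol enrols 70, which leaves a margin. Where r exceeds 0.5, using 0.154 for a change score is conservative. If allocation is random, the unadjusted t-test is valid, so ANCOVA is an improvement in efficiency and not the repair of an invalid test.

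All of this stands, and it limits the point. A reader might infer that 50 per group is correct only at one particular correlation, or that the trial is underpowered. The documents support neither. The first applies only to a change-score test, which Statistical Methods does not name. The second depends on r, on the true SD and on which analysis is used.

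The reply does not remove the mismatch between the difference in change in the sample-size section and the values tested, nor the missing power and sidedness. It also relies on random allocation, which the design section contradicts.

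**Conclusion.** The point holds in this form: the quantity sized and the quantity tested differ, the power claim lacks inputs it needs, and baseline nPCR is left unused.

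The gain from adjustment should be measured against the planned test. At SD 0.154 and 50 per group it is from 82% to between 84% and 98% for r from 0.2 to 0.7. The lower change-score figures (63% at r = 0.2) matter if change from baseline, which the sample-size section targets and the efficacy section also lists as an expected outcome, becomes the reported analysis.

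These figures assume equal SDs at both visits, random allocation and a true SD of 0.154. Two further inferences go too far:
- That adjustment settles the allocation problem. If groups follow patient willingness, ANCOVA reduces the bias from baseline PCR imbalance but does not remove self-selection. The precision formula no longer strictly applies, and ANCOVA and change scores can estimate different effects.
- That with ANCOVA the present numbers are sure to be enough. The pilot SD interval of 0.106 to 0.281 does not allow that assurance.

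**What to change.** 1. In Statistical Methods and the SAP, name one PCR analysis: ANCOVA of 12-month nPCR on group with baseline nPCR as covariate. Report the adjusted mean difference with its 95% CI, in place of the unadjusted t-test or rank-sum test for this endpoint.
2. Restate the sample-size section for that analysis, giving sidedness, power and a range of assumed r. Identify 0.154 as a single-visit SD from 10 patients with 95% CI 0.106 to 0.281, and give no assurance that the number of patients is sufficient across that interval.
3. Reconcile the design section (assignment by willingness) with the intervention description (random assignment), and state what the adjusted difference can be taken to mean under the method actually used.

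The cost is wording only: baseline nPCR is already collected, and no extra visits or data are needed. The restated power claim may look less favourable once the uncertainty in the SD is shown. The change should be made before PCR results by group are seen.
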